- Blood sampling for A3907, and serum total and individual bile acids ([Section 9.5.1](#))
- Urine pregnancy test for WOCBP
- AE monitoring ([Section 9.3.4](#))
- Document concomitant medications ([Section 9.3.1](#))
- Clinical chemistry, hematology, and urinalysis ([Section 9.3.5](#))
- Stool sample for faecal calprotectin ([Section 9.3.11](#))

Study Day 42/Visit 5

The following procedures and assessments will be conducted:

- Physical examination ([Section 9.3.2](#)) and vital signs ([Section 9.3.3](#))
- Study drug administration
- Study drug compliance ([Section 8.4](#))
- Review of Patient Diary for compliance (e.g. mood Likert Scale, and pruritus [as applicable], fatigue, and sleep disturbance NRS) and distribution of next diary.
- Blood sampling for A3907, FGF-19, C4, biomarkers, and serum total and individual bile acids ([Section 9.5.1](#))
- Collect 24-hour urine sample for bile acid assessment ([Section 9.5.1](#))
- Urine pregnancy test for WOCBP
- AE monitoring ([Section 9.3.4](#))
- Document concomitant medications ([Section 9.3.1](#))
- Clinical chemistry, hematology, coagulation, and urinalysis ([Section 9.3.5](#))

- 12-lead ECG ([Section 9.3.7](#))
- Fibroscan ([Section 9.3.8](#))
- Stool sample for faecal calprotectin ([Section 9.3.11](#))

Study Day 70/Visit 6

The following procedures and assessments will be conducted:

- Vital signs ([Section 9.3.3](#))
- Study drug administration
- Study drug compliance ([Section 8.4](#))
- Review of Patient Diary for compliance (e.g. mood Likert Scale, and pruritus [as applicable], fatigue, and sleep disturbance NRS) and distribution of next diary.
- Blood sampling for A3907 and serum total and individual bile acids ([Section 9.5.1](#))
- Urine pregnancy test for WOCBP
- AE monitoring ([Section 9.3.4](#))
- Document concomitant medications ([Section 9.3.1](#))
- Clinical chemistry, hematology, and urinalysis ([Section 9.3.5](#))
- Stool sample for faecal calprotectin ([Section 9.3.11](#))

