 - b. liver stiffness measurement, assessed by FibroScan (FibroScan value > 14.4 kPa), in addition to clinical assessment and biochemical markers at the discretion of the investigator.
 - c. signs and symptoms of hepatic decompensation (including, but not limited to, jaundice, ascites, variceal haemorrhage, and/or hepatic encephalopathy).
15. History of bacterial cholangitis within 60 days prior to the Screening Period, or if the patient is on antibiotics for prophylaxis of recurrent cholangitis.
16. Females who are pregnant, lactating, or breast feeding as detailed in [Section 9.3.18](#).
17. History of alcohol or substance abuse in the previous 2 years. Patients must agree to refrain from illicit drug (including marijuana) and alcohol use during the study.
18. Hypersensitivity to investigational medicinal product (A3907) and its excipients.
19. Presence of any contraindication for undergoing MRCP (e.g. pacemaker).
20. Any other condition or abnormality which, in the opinion of the investigator (or designee), may compromise the safety of the patient or interfere with the patient participating in, or completing the study.

Treatment Exclusions:

21. Administration of medications that slow gastrointestinal motility ([Section 8.6.2](#)).
22. Treatment with rifampicin.

23. Exposure to oral drugs that are strong inhibitors or inducers of CYP3A4 enzymes (e.g. grapefruit juice, ritonavir, itraconazole, ketoconazole, troleandomycin, rifampin, St John's wort, etc.) within 14 days prior to the Screening Period, or 5 half-lives of the drug, whichever is longer ([Section 8.6.2](#)).
24. Exposure to oral drugs that are substrates of CYP3A4 enzymes (e.g. codeine, ciclosporin [cyclosporin], diazepam, etc.) during the study ([Section 8.6.2](#)).
25. Treatment with vitamin D or fibrates, unless patient is on a stable dose ≥ 6 months prior to baseline.
26. Exposure to an investigational drug, biologic agent, or medical device within 30 days prior to the Screening Period, or 5 half-lives of the study agent, whichever is longer.

Laboratory Exclusions:

27. Platelet count $< 150\,000/\text{mm}^3$.
28. Albumin level $< 3.0\text{ g/dL}$.
29. INR > 1.3 (the patient may be treated with vitamin K intravenously, and if INR is ≤ 1.3 at resampling, the patient may be enrolled).
30. Medical conditions that may cause non-hepatic increases in ALP (e.g. Paget's disease). A GGT or ALP isoenzymes should be obtained for confirmation of biliary origin;

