9.3.6 Individual Patient Safety Monitoring

9.3.6.1 Liver Monitoring

Strategies to monitor markers of liver disease throughout the study are outlined below where the ULN will be based on central laboratory reference values. To make the distinction among the type of injury, and to make a causality assessment, the Roussel Uclaf Causality Assessment Method ([Appendix 2](#)) will be used.

For abnormalities classified as hepatic adverse events and/or hepatic decompensation, a PK sample should be collected as close to the onset of the event as possible.

If isolated transaminase elevations are observed, defined as:

Normal bilirubin AND absence of clinical hepatitis symptoms AND

- ALT or AST $\geq 5 \times$ ULN (if normal at baseline) OR
- ALT or AST $\geq 3 \times$ baseline (if abnormal at baseline) or > 500 U/L, whichever comes first

Then:

- a. Repeat liver profile (AST, ALT, bilirubin, and prothrombin time [PT] or INR) within 2 to 3 days
- b. Evaluate creatine phosphokinase (CPK) and lactate dehydrogenase (LDH)
- c. As needed (for example, persistent ALT/total bilirubin elevation or worsening of liver function), consider evaluation for alternative etiologies

Monitor the patient using the close observation guidelines found below.

If any ONE of the following criteria are met:

1. Transaminases (ALT or AST $\geq 3 \times$ baseline or 500 U/L, whichever comes first) AND bilirubin (total bilirubin $> 2 \times$ ULN) elevations
2. Transaminase elevations alone (ALT or AST $> 10 \times$ ULN or $5 \times$ baseline or absolute threshold of 800 U/L, whichever comes first) in presence of normal LDH and CPK
3. Total bilirubin increased, unrelated to hemolysis (elevated reticulocyte count) or established genetic diseases, such as Gilbert's syndrome

- a. Doubling if total bilirubin was < 3 mg/dL (equivalent to $51.3 \mu\text{mol/L}$) at baseline
OR
 - b. Increase by > 3 mg/dL (equivalent to $51.3 \mu\text{mol/L}$) if total bilirubin was ≥ 3 mg/dL (equivalent to $51.3 \mu\text{mol/L}$) at baseline
4. INR increase refractory to vitamin K administration
- a. Increase by > 1.5 if INR was normal at baseline OR
 - b. Increase by > 0.4 if INR was abnormal at baseline
5. Any increase in total bilirubin and transaminases if accompanied by EITHER a symptom of clinical hepatitis (e.g. vomiting, nausea, right upper quadrant pain) OR immunological reaction (rash or $> 5\%$ eosinophilia)

Then:

- a. Interrupt study medication

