9.3.10 MELD Score

The MELD Score will be calculated as follows:

$$\text{MELD Score} = 9.57 \times \ln(\text{creatinine mg/dL}) + 3.78 \times \ln(\text{total bilirubin mg/dL}) + 11.2 \times \ln(\text{INR}) + 6.43$$

The MELD Na Score will be calculated as follows:

$$\text{MELD Na Score} = \text{MELD} - \text{Na} - [0.025 \times \text{MELD} \times (140 - \text{Na})] + 140$$

Laboratory values less than 1.0 will be set to 1.0 and serum creatinine values greater than 4.0 mg/dL (equivalent to 353.6 µmol/L) will be set to 4.0 for calculation of the MELD score.

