9.2. Clinical Laboratory Evaluations

Clinical safety laboratory evaluations will be performed by a central laboratory. Samples will be collected for clinical laboratory evaluations at timepoints indicated in [Table 1](#) and [Table 2](#). Safety lab parameter like clinical chemistry and urinalysis ([Appendix 2](#)) will be presented from Baseline up to Follow-Up after 12-Week Treatment. Hematology will be presented at Baseline, Start of 12-Week Treatment up to Follow-Up after 12-Week Treatment. Coagulation will be presented at Baseline, Start of 12-Week Treatment, Week 4 of 12-Week Treatment and Week 12 of 12-Week Treatment.

Descriptive statistics for clinical laboratory values [chemistry, hematology, urinalysis, coagulation laboratory tests, LBTs including aminotransferase (ALT and AST), GGT, ALP, and total and direct bilirubin levels] will be presented. For LBTs, 2-sided 95% CI of the mean for relative and absolute change from baseline 1 to each post-baseline visit and the last visit, and actual values at each visit will be presented along with descriptive statistics. Relative and absolute changes from baseline 1 to each post-baseline visit and the last visit will also be presented for quantitative variables. For clinical chemistry assessments and urinalysis tests with quantitative results, baseline 1 is defined as the average of all Screening results and results on the day of the planned single dose if both results are available. Otherwise, baseline 1 will be defined as the last non-missing assessment prior to the study drug administration of planned single dose. For other laboratory parameters, baseline 1 is defined as the last non-missing assessment of that parameter prior to the study drug administration of planned single dose. For categorical variables (i.e., normal or abnormal findings, or qualitative clinical laboratory tests), a table of categorical values over time will be presented. Results of quantitative clinical laboratory values will be categorized as low, normal, or high according to laboratory range specifications. Shifts from baseline 1 to each scheduled post-baseline time point will be presented to show the number and percentage of patients in each category by parameter.

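### Liver interruption criterion 4 sets a higher INR trigger for a normal baseline than for an abnormal one, with a drop of 1.1 INR units at the upper limit of normal

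*Protocol*

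**What the plan says.** Protocol 9.3.6.1 lists five criteria, any one of which interrupts study drug and starts a work-up for drug-induced liver injury. Criterion 4 concerns an "INR increase refractory to vitamin K administration". It has two limbs: "Increase by > 1.5 if INR was normal at baseline OR" and "Increase by > 0.4 if INR was abnormal at baseline". The section takes upper limits of normal from the central laboratory, prints no INR range, and does not say which visit supplies the baseline.

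Exclusion 29 (Protocol 7.2.3) bars entry with INR above 1.3 in every arm. It allows one remedy: "the patient may be treated with vitamin K intravenously, and if INR is ≤ 1.3 at resampling, the patient may be enrolled".

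SAP 9.2.1 copies both limbs into the definition behind its count of patients with an abnormal liver test and its listing of patients who meet the DILI criteria. It refers only to baseline. For coagulation, SAP 9.2 points to baseline 1: "For other laboratory parameters, baseline 1 is defined as the last non-missing assessment of that parameter prior to the study drug administration". In SAP Table 2 that is the Visit 1 value.

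**The concern.** A patient who starts with normal coagulation has to reach a much worse INR before drug is interrupted than a patient who starts slightly abnormal. That ordering is the reverse of what a safety threshold should give. A refractory rise from 1.0 to 2.4 would not fire the rule, while a rise from 1.3 to just above 1.7 would. The rule also sits awkwardly beside exclusion 29, which refuses entry to anyone whose INR stays above 1.3 after vitamin K.

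Safety is the primary objective, and the protocol describes this as the first use of A3907 in patients with PSC, with unknown risks. None of the other four interruption criteria uses INR, so nothing else in the list covers a refractory INR rise that occurs alone.

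**Working it through.** **Inputs.** Increments of 1.5 (normal baseline) and 0.4 (abnormal baseline) come from Protocol 9.3.6.1. The entry cap of 1.3 comes from exclusion 29. The normal INR range is my assumption: 0.9 to 1.1, widened to 0.8 to 1.3 as a check. The plan states no absolute trigger, so there is no figure to reproduce.

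**Reading.** Both limbs are additive. A rise of 0.4 cannot be a multiplier, and the same list writes multiples as a factor times baseline or as a doubling.

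**Boundary, with no assumed range.** Trigger = baseline + increment. A baseline exactly at the ULN fires above ULN + 1.5. A baseline just over the ULN fires just above ULN + 0.4. The drop is 1.5 − 0.4 = 1.1 INR units for any ULN.

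**Absolute triggers.**

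| Baseline INR | If normal, fires above | If abnormal, fires above |
|---|---|---|
| 0.8 | 2.3 | – |
| 0.9 | 2.4 | – |
| 1.0 | 2.5 | – |
| 1.1 | 2.6 | 1.5 |
| 1.2 | 2.7 | 1.6 |
| 1.3 | 2.8 | 1.7 |

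Whether 1.1 to 1.3 counts as normal depends on the central laboratory. The ceiling for an abnormally high entry baseline, 1.3 + 0.4 = 1.7, needs no such assumption. If the ULN is 1.3 or more, no entrant has a high baseline, and everyone falls under the less sensitive limb.

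**If baseline is not the entry value.** A later baseline is not capped at 1.3. The order stays reversed whenever abnormal baseline + 0.4 < normal baseline + 1.5, that is, when the abnormal baseline is less than 1.1 above the normal one. Against a normal 1.0, this means any abnormal baseline below 2.1.

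**Comparison with criterion 3.** The bilirubin rule also has two limbs, split at 3 mg/dL. Doubling just below 3 approaches 6, and adding 3 at a baseline of 3 gives 6. The limbs join, and a worse baseline never gets a lower trigger.

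**Check of the fix.** Set the normal limb to INR above ULN + 0.4. For ULN 1.0/1.1/1.2/1.3 this is 1.4/1.5/1.6/1.7. Any abnormal baseline exceeds the ULN, so its trigger exceeds ULN + 0.4 and the order is right. A normal baseline is at most the ULN, so the rise it needs is at least 0.4. A flat 1.5 fits less well at both ends. At ULN 1.0 it exceeds the lowest abnormal trigger (just above 1.4) by about 0.1. At ULN 1.3 a normal baseline of 1.3 would fire after a rise of just over 0.2.

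**The case against.** The strongest defence is that a tighter rule for already abnormal patients may be deliberate. The isolated-transaminase step in the same section is ordered that way: 5 × ULN from a normal baseline against 3 × baseline from an abnormal one, so a baseline of 1.1 × ULN fires at 3.3 × ULN. But that step prompts only repeat tests and closer observation, and its order reverses only for baselines below 5/3 = 1.67 × ULN. It does not justify the ordering of an interruption rule whose order is reversed for every abnormally high entry baseline.

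It is also fair that the documents give no INR range. The 2.4 to 2.6 figure is conditional, and the number of patients with an abnormal entry baseline is unknown. The 1.1-unit drop and the 1.7 ceiling do not depend on that range.

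Other safeguards stand. Criteria 1, 2, 3 and 5 interrupt drug if transaminases or bilirubin qualify. A RUCAM score meeting DILI criteria requires discontinuation, the investigator may withdraw a patient at any time, and the SRC reviews laboratory data. A reader might infer that patients are left unprotected; the documents do not support that.

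A reader might also add the visit schedule to the charge. Coagulation is drawn at Visits 1, 3, 5 and 7. Visits 4 and 6 list only "Clinical chemistry, hematology, and urinalysis", which leaves 98 − 42 = 56 days between the last two scheduled draws. That does not enlarge the point. A rise shown to be refractory has normally already had vitamin K and a repeat INR, Protocol 9.3.5 allows extra samples, and the gap is the same at any threshold. Converting the triggers into MELD points would add little, because MELD is calculated in Arm 4 only.

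**Conclusion.** The threshold is wrong as written: followed literally, it gives the healthier baseline the more permissive rule. The size is 1.1 INR units at the boundary, whatever the ULN. In absolute terms the normal limb fires above 2.4 to 2.6 for an assumed normal baseline of 0.9 to 1.1 (2.3 to 2.8 for 0.8 to 1.3), against 1.7 at most for an abnormally high entry baseline. The 1.7 figure assumes that baseline is the entry value.

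The exposed case is narrow: an isolated, vitamin K-refractory INR rise that meets none of criteria 1, 2, 3 or 5. Its frequency cannot be estimated from the documents.

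Two stronger readings should be resisted. A reader might conclude that *by* is a slip for *to*. That is plausible, but the SAP carries the same wording and nothing in either document settles it. A reader might also infer that such patients vanish from the analysis. They would be absent from both the DILI count and the DILI listing in SAP 9.2.1, but the general coagulation summaries, shift tables and laboratory listings would still show their values: "Coagulation will be presented at Baseline, Start of 12-Week Treatment, Week 4 of 12-Week Treatment and Week 12 of 12-Week Treatment".

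**What to change.** 1. In Protocol 9.3.6.1, change the normal-baseline limb to an absolute INR above ULN + 0.4. This uses the protocol's own increment and joins the abnormal limb without reversal. If the sponsor confirms that *by* was written for *to*, INR above 1.5 is the alternative, after checking it against the central laboratory ULN.
2. State there that baseline is the last INR before the single dose, which matches baseline 1 in the SAP.
3. Carry the corrected limb into SAP 9.2.1 so that both the DILI count and the DILI listing pick up these patients.
4. The documents do not say whether dosing has finished, but the planned period ends in 2025 and the SAP cites a March 2025 drug dictionary. If dosing is complete, keep the count under the existing rule and add the corrected INR limb as a separate row.

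The transaminase criteria can stay as they are.

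The cost is a short amendment or clarification, matching SAP text, and at most one added row. No new data are needed, because INR is already listed as a coagulation parameter. The SAP does need a working rule for *refractory*, taking vitamin K use from concomitant medications. The clinical downside is possibly a few more interruptions, confined to refractory INR values between about 1.4 (ULN 1.0 + 0.4) and 2.8 (baseline 1.3 + 1.5).

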9.3.6.2 De-challenge/Re-challenge for Liver and Clinical Hepatitis Monitoring

Re-challenge is not recommended if:

- If a patient has had possible/probable drug-induced liver injury according to RUCAM score.
- If a decompensation event has occurred (i.e. variceal haemorrhage, ascites, hepatic encephalopathy, etc.).

If an event is assessed as due to underlying cholestatic liver disease variability or another alternative aetiology is identified AND liver tests returned to baseline, re-challenge may be considered after consultation with the sponsor medical monitor.

If the ALT/total bilirubin elevations are observed after re-challenge, then repeat re-challenge is discouraged.

If a patient is permanently discontinued, monitoring should be continued as outlined in [Section 9.3.6.4](#).

9.3.6.3 Diarrhoea

Study drug should be discontinued if a patient develops diarrhoea with at least 1 of the following concomitant signs or symptoms: grossly bloody stools, vomiting, dehydration requiring treatment with oral or intravenous rehydration and/or electrolyte imbalances, fever ($\geq 38^{\circ}\text{C}$) and/or the diarrhoea persists for 7 or more days.

If there is gross blood in stool, INR and platelets should be measured.

Study drug will be reintroduced when the symptoms have resolved. If the diarrhoea re-occurs within 1 week after the re-challenge with no alternate etiology, the patient will be permanently discontinued and monitored as outlined in [Section 9.3.6.4](#).

9.3.6.4 Monitoring after Permanent Discontinuation of Study Drug Due to Safety

Once study drug is permanently discontinued for hepatic, gastrointestinal (e.g. diarrhoea), or other severe AE related to study drug, the patient will be monitored weekly until the laboratory and clinical parameters have normalised/stabilised.

9.3.7 Electrocardiogram

Standard resting 12-lead ECGs will be recorded after the patient has been supine and at rest for at least 5 minutes and at least 5 minutes prior to blood sample collections at visits indicated in the Schedule of Assessments ([Table 1](#)) and when judged to be clinically

appropriate. The investigator (or designee) will perform a clinical assessment of each 12-lead ECG.

The PR, RR, QT, and QTcF intervals; QRS duration; and heart rate will be collected.

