In a first-in-human (FIH) study (Study A3907-001), A3907 or matching placebo were administered in capsules to healthy subjects as single oral doses of C to C mg or CCI oral doses of CCI mg for 7 days. Overall, A3907 was well tolerated when administered as single and multiple ascending doses (SAD/MAD) to the healthy subjects. There were no serious adverse events (SAEs), all treatment-emergent adverse events (TEAEs) were mild in

severity, and no subjects discontinued study drug or withdrew from the study due to TEAEs. The only treatment-related AEs that occurred in ≥ 2 subjects following single or multiple doses of A3907 were diarrhoea, abdominal pain, and headache. Pharmacokinetic analysis revealed that, with this formulation, A3907 was slowly absorbed (T_{\max} approximately [REDACTED] hours) and dose proportionality was demonstrated at single doses of [REDACTED]; the higher single dose of [REDACTED] mg did not result in increased exposure. No accumulation was seen following multiple [REDACTED] doses of [REDACTED] mg for 7 days, consistent with a half-life of approximately [REDACTED] hours. An increase in serum C4 concentrations and a decrease in serum LDL-C concentrations was observed at all A3907 doses; exploratory PK/pharmacodynamics (PD) results suggested a weak correlation between these PD parameters and A3907 PK parameters. While no clear trends were seen between A3907 concentrations and serum total bile acid concentrations, there was a decrease in total urine bile acids excreted at all treatment doses compared to placebo. Together, results of this study suggest that A3907 does inhibit ASBT but the net effect in the intended population is yet to be determined.

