- ^h Plasma PK samples for Arm 1+2 will be obtained on Day 0 (Visit 2) and Day 98 (Visit 7) pre-dose and at 0.5, 1, 1.5, 2, 4, 6, 8 and 10 hours post-dose (\pm 5 minutes). Plasma PK samples for Arm 3+4 will be obtained on Day 0 (Visit 2) pre-dose and at 0.5, 1, 1.5, 2, 4, 6, 8, 12 and 24 hours post-dose (\pm 5 minutes). The 12-hour sample collection will be obtained post administration of the first BID dose, but before administration of the second BID dose, and the 24-hour sample collection will be obtained before study drug administration the following morning. On Day 98 (Visit 7), PK samples for Arm 3+4 will be obtained pre-dose and at 0.5, 1, 1.5, 2, 4, 6, 8, and 10 hours post-dose (\pm 5 minutes). The post-dose sample collections will be obtained post administration of the first BID dose. Sampling timepoints at Day 98 (Visit 7) may be adjusted based on observed data from Day 0 (Visit 2) without changing the total number of blood samples. For Visits 3 to 6 (inclusive), PK will be collected once pre-dose, and once for Visit 8. In the case of hepatic adverse events and/or hepatic decompensation, a PK sample should be collected as close to the onset of the event as possible. In the case of hepatic adverse events and/or hepatic decompensation, a PK sample should be collected as close to the onset of the event as possible.
- ⁱ Metabolites (MIST) samples will be obtained on Day 0 (Visit 2) and Day 98 (Visit 7) pre-dose, 2, 4, 8 and 12 hours post dose (\pm 5 minutes). Sampling timepoints may be adjusted based on observed data from Day 0 (Visit 2) without changing the total number of blood samples.
- ^j Serum bile acid levels will be obtained once per applicable visit, pre-dose. Serum bile acid levels will be obtained once on Visit 8.
- ^k Serum samples for C4 and FGF-19 will be obtained once per applicable visit, pre-dose.
- ^l Biomarkers include autotaxin, ProC3, hsCRP, MMP7, MMP9, ELF score, AFP and CA 19-9. Serum samples will be obtained once per applicable visit—pre-dose. Serum samples will be obtained once on Visit 8.
- ^m Urine will be collected by the patient for the 24-hour period prior to study visit.

- ⁿ The safety laboratory parameters to be assessed are presented in [Table 2](#).
- ^o Confirmatory FSH for women of WONCBP upon Screening.
- ^p Serum pregnancy test for all women upon Screening.

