- ^q Urine pregnancy tests for WOCBP should be done at Visit 2 through Visit 8. A point of care urine dipstick for pregnancy will be obtained. If the results are positive for pregnancy, a hCG blood pregnancy test will be performed.
- ^r The 12 lead ECG should be performed with the patient in supine rest for at least 5 minutes prior to blood sample collection.
- ^s Performed where available, as per institution standard practice.
- ^t MRCP is only applicable for patients without MRCP or ERCP results available <6 months prior to Screening.
- ^u Site staff will assess pruritus at the Screening Visit by having patients respond to a dichotomous yes/no question asking if they have “experienced pruritus in the past 7 days.”
- ^v Patient Diary will include pruritus NRS and/or fatigue NRS, sleep disturbance NRS, mood Likert scale, and study drug compliance and will be completed daily and collected at each study visit. Pruritus NRS will be completed in the patient diary only for patients that report experiencing pruritus at the Screening Visit. Diary compliance review to be performed at Visit 2 to Visit 8.
- ^w Stool samples will be collected at home for patients with inflammatory bowel disease. Sampling kits will be provided to patients for at-home collection.

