On clinic visit days when laboratory assessments are conducted, study drug should be taken at the clinic after samples are collected. Patients will be required to fast for 4 hours prior to these study visits and breakfast will be provided at the time the study drug is administered. The first of the BID doses will be administered at the clinic and patients will be instructed to take the second of the BID doses at home, 12 hours after the first dose was received.

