9.4 Pharmacokinetic Assessments

Pharmacokinetic blood samples will be collected according to the schedule in [Table 1](#). Samples for Arms 1+2 will be obtained on Day 0 (Visit 2) and Week 12 (Visit 7) pre-dose and at 0.5, 1, 1.5, 2, 4, 6, 8, and 10 hours post-dose (\pm 5 minutes). Samples for Arms 3+4 will be obtained on Day 0 (Visit 2) pre-dose at 0.5, 1, 1.5, 2, 4, 6, 8, 12, and 24 hours post-dose (\pm 5 minutes). CCI

CCI

CCI Samples for Arms 3+4 will be obtained on Day 98 (Visit 7) pre-dose and at 0.5, 1, 1.5, 2, 4, 6, 8, and 10 hours post-dose (\pm 5 minutes). The post-dose sample collections will be obtained post administration of the first BID dose. For Visits 3 to 6 (inclusive), PK will be collected once pre-dose, and once for Visit 8. Sampling timepoints at Week 12 (Visit 7) may be adjusted based on observed data from Day 0 (Visit 2) without changing the total number of blood samples.

All pre-dose samples should be taken immediately before the administration of study drug. Patients will fast for 4 hours before study visit (only water permitted). Blood samples will be processed for collection of plasma fractions for determination of A3907 concentrations and banked for exploratory assessment of MIST (Visit 2 and Visit 7 only). In addition, a blood sample for PK analysis should be collected, if possible, at the time of any SAE.

A PK sample collection manual will be provided to instruct the type of anticoagulant, material supplies, and sample processing, storage, and shipping procedures. Plasma samples will be shipped to the analytical laboratory for analysis.

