9.5. Electrocardiogram results

Standard resting 12-lead electrocardiograms (ECGs) will be recorded after the patient has been supine and at rest for at least 5 minutes at the times indicated in the Schedule of Assessments and when judged to be clinically appropriate. The investigator (or designee) will perform a clinical assessment of each 12-lead ECG. The PR, RR, QT and QTcF intervals; QRS duration; and heart rate will be presented.

An overall 12-lead ECG interpretation (Normal, Abnormal Not Clinically Significant, Abnormal Clinically Significant) will be available based on central reading of ECG data. Shifts from baseline 1 to each scheduled post-baseline time point will be presented to show the number and percentage of patients in each category by treatment for patients in the Safety Analysis Set.

A shift table for ECG interpretation will present the shift from baseline 1 to each post-baseline assessment. Patients will be summarised by treatment arms.

Descriptive statistics for observed values at each time point and absolute changes from baseline 1 will be summarised for heart rate (beats/min), PR interval (msec), RR Interval (msec), QRS duration (msec), QT interval (msec), corrected QT interval based on Fridericia's formula (QTcF) (msec) at each scheduled visit. ECG interpretation results (normal; abnormal not clinically significant; abnormal clinically significant) will be presented as the number and percentage of patients in each category at scheduled visits. Patients will be summarised by treatment arm.

All ECG results will be presented in a listing.

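### No scheduled on-treatment ECG is assigned to a post-dose time, so the ECG summary may miss an effect at or near peak concentration, most clearly in the once-daily arms

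*Protocol*

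**What the plan says.** Table 1 (Protocol 7.1.2) schedules one 12-lead ECG at each of Visits 1, 2, 5 and 7. Visits 5 (Day 42) and 7 (Day 98) are the only ones during repeat dosing.

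- **ECG before blood.** Section 9.3.7 asks for the ECG "at least 5 minutes prior to blood sample collections at visits indicated in the Schedule of Assessments". Table 1 footnote r gives the same order more loosely: "The 12 lead ECG should be performed with the patient in supine rest for at least 5 minutes prior to blood sample collection".
- **Blood before dose.** Section 8.2: "On clinic visit days when laboratory assessments are conducted, study drug should be taken at the clinic after samples are collected". Section 9.4: "All pre-dose samples should be taken immediately before the administration of study drug".
- **PK draws.** Footnote h: "For Visits 3 to 6 (inclusive), PK will be collected once pre-dose, and once for Visit 8". In Arms 1 and 2, serial samples "will be obtained on Day 0 (Visit 2) and Day 98 (Visit 7) pre-dose and at 0.5, 1, 1.5, 2, 4, 6" (the list of times continues, with the last draw 10 h after dosing). Arms 3 and 4 have the same post-dose times on Day 98.
- **Analysis.** SAP 4.5, Table 2, labels the Visit 2 ECG as a pre-dose baseline and assigns later ECGs to visits by study day. SAP 9.5: "Descriptive statistics for observed values at each time point and absolute changes from baseline 1 will be summarised for heart rate", and likewise for PR, RR, QRS, QT and QTcF, with shift tables of the overall interpretation. It uses neither time after dose nor plasma concentration.
- **Unscheduled ECGs.** Section 9.3.7 also allows ECGs on clinical judgement, at no set time.

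**The concern.** An ECG effect that follows plasma concentration is largest at or near Cmax. If every planned on-treatment reading comes just before the next dose, the change-from-baseline table describes the low end of the dosing interval. A reader could still take a flat table as reassurance across the whole interval.

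This matters because safety is the primary objective and ECG is one of the listed safety analyses. It is the first use of the drug in PSC, and Section 5.5 calls the risks in this population unknown. Section 5.4 expects individual PK to vary with liver impairment and food, and the formulation has changed to a tablet. The protocol treats peak exposure as a safety quantity: Section 7.2.4.1 stops dosing when Cmax or AUC exceeds the first-in-human range. Yet no ECG is timed to that peak.

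**Working it through.** The plan gives no figure to reproduce: it has no power calculation and no stated ECG-to-dose interval. The check traces the order of events and then gives a sense of scale.

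**Step 1. Order of events at each ECG visit on or after the dosing day**

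| Visit | Blood draws that day | ECG position relative to dose |
|---|---|---|
| 2 (Day 0) | Pre-dose, then serial | Pre-dose (SAP Table 2 says so) |
| 5 (Day 42) | Pre-dose only | Trough: about 24 h after the last QD dose, 12 h after the last BID dose |
| 7 (Day 98) | Pre-dose, then 0.5 to 10 h | Not explicit; pre-dose if the ECG precedes the first draw |

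The chain is firm at Visit 5 and an inference at Visit 7. Section 7.1.3.2 lists the Visit 2 ECG twice while Table 1 has one mark. That should be reconciled, but it does not establish a post-dose ECG.

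**Step 2. Trough as a share of peak (assumed PK)**

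Half-life and Tmax are redacted, so I assumed a one-compartment model with first-order absorption at steady state:

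C(t) ∝ e^(−kt)/(1 − e^(−kτ)) − e^(−ka·t)/(1 − e^(−ka·τ)), with k = ln 2 / half-life.

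The ratio is C(τ) divided by the maximum of C(t), with τ = 24 h (QD) or 12 h (BID).

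| Half-life (assumed) | ka per h (assumed) | QD trough/peak | BID trough/peak |
|---|---|---|---|
| 4 h | 0.7 | 3% | 25% |
| 4 h | 0.3 | 7% | 44% |
| 6 h | 0.7 | 11% | 40% |
| 6 h | 0.3 | 18% | 58% |
| 8 h | 0.7 | 19% | 51% |
| 8 h | 0.3 | 27% | 66% |

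Single-dose Tmax over this grid, ln(ka/k)/(ka − k), is 2.7 to 5.8 h.

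**Step 3. Fit with the first-in-human statement**

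Section 5.2.3 reports: "No accumulation was seen following multiple" doses (regimen redacted). The QD accumulation ratio is 1/(1 − e^(−24k)), which is 1.02 at a half-life of 4 h and 1.14 at 8 h. If no accumulation means a ratio of at most 1.1 on daily dosing (an assumption), then e^(−24k) ≤ 1 − 1/1.1 = 0.091. The half-life is then at most 24 × ln 2 / 2.40 = 6.9 h.

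**Step 4. Sensitivity**

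With half-life from 2 to 24 h and absorption half-life from 0.5 to 1.5 h, trough is 0.1 to 61% of peak on QD dosing and 3 to 83% on BID dosing. The longest half-lives imply QD accumulation ratios of 1.33 (12 h) and 2.00 (24 h), which fit the first-in-human statement poorly.

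**Step 5. What one ECG per visit can show**

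The 95% CI half-width for a mean QTcF change with n = 6 is 2.571 × SD/√6. That is 10.5, 15.7 and 21.0 ms for assumed SDs of 10, 15 and 20 ms.

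**The case against.** The strongest reply is that the protocol never says every ECG is pre-dose. Section 9.3.7 and footnote r order the ECG against blood collection only. Vital signs, by contrast, carry an explicit instruction to measure before A3907. An ECG taken five minutes before the 4 h draw at Visit 7 would comply, and the rule that dosing follows sampling cannot apply literally to post-dose samples. This stands: a trough reading at Visit 7 is the natural inference, not a stated fact. It is also a reason to fix the text, since sites could record Visit 7 ECGs at different times after dose and the SAP would pool them unlabelled.

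A reader might also infer that a concentration-related ECG effect cannot be seen at all. The documents do not support that. A sustained or delayed effect could appear at trough, twice-daily troughs may be a sizeable share of peak, and clinically driven ECGs are allowed.

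Four further points limit the weight of the concern:

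- The primary endpoint is TEAE incidence; ECG intervals are supporting descriptive data.
- Patients whose Day 0 exposure exceeds the first-in-human maximum do not continue, and Section 5.2.3 reports safety pharmacology without effects of concern.
- SAP 8.1 places PK analyses in separate plans, so an exposure-ECG analysis may exist elsewhere.
- A post-dose ECG would be fed and later in the day, set against a fasting pre-dose baseline.

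All four stand. They make this a modest improvement to the plan, but none of them assigns an ECG to a post-dose time.

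**Conclusion.** The point holds in a limited form. Visit 2 is a pre-dose baseline, Visit 5 is at trough, Visit 7 is unspecified but most naturally pre-dose, and no scheduled on-treatment ECG is assigned to a post-dose time. The planned summaries may therefore miss a QTcF, PR, QRS or heart-rate effect near peak, most clearly in Arms 1 and 2.

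The peak-to-trough gap cannot be fixed from the documents. The ranges of 3 to 27% (QD) and 25 to 66% (BID) rest on assumed half-lives of 4 to 8 h and assumed absorption rates. The first-in-human statement that makes them plausible comes from capsules in healthy subjects. It would be wrong to conclude that all ECGs are fixed at trough, or that moving one would allow a small QTc effect to be excluded: the Step 5 half-widths of 10 to 21 ms, with no control arm, rule that out.

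**What to change.** **Protocol 9.3.7 and Table 1 footnote r.** State the ECG time relative to dose at Visits 2, 5 and 7. Place the Visit 7 ECG just before a post-dose PK draw near the Tmax observed on Day 0. Footnote h already allows Day 98 sampling times to be adjusted from Day 0 data. Reconcile the duplicate Visit 2 entry in 7.1.3.2 with the single mark in Table 1.

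**SAP 9.5.** Label every ECG, including unscheduled ones, by time after dose. Keep Visit 5 as the like-for-like trough comparison with baseline. List or plot the Visit 7 QTcF change with the concurrent A3907 concentration.

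**Cost.** No extra visit, ECG or blood sample is needed: the reading moves within a visit that already has 10 h of sampling, and the analysis work is minor. The Week 12 trough ECG is lost. The Visit 7 change will mix drug with meal and time-of-day effects, so it should be described as a screen for large effects.

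**If Visit 7 is not moved, or those visits are already done.** Add a sentence to the SAP and the report that the scheduled ECGs describe trough exposure and give no reassurance at Cmax, and report the actual time after dose where it was recorded.
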